3.2 Exclusion Criteria

Subjects are excluded from the study if any of the following criteria apply:

1. Has received prior therapy with an anti-PD-1, anti-PD-L1, or anti-PD-L2 agent or with an agent directed to another stimulatory or co-inhibitory T-cell receptor (e.g., CTLA-4, OX-40, CD137).
2. Prior therapy with a PI3K inhibitor

3. Has received prior chemotherapy, targeted small molecule therapy, or surgery within 4 weeks of the first dose of treatment. Participants must have recovered from all AEs due to previous interventions to \leq Grade 1 or baseline. Participants with \leq grade 2 neuropathy, anemia, and/or alopecia may be eligible.
4. Has received prior radiotherapy within 2 weeks of start of study treatment. Participants must have recovered from all radiation-related toxicities to \leq Grade 1 or baseline, not require corticosteroids, and not have had radiation pneumonitis. A 1-week washout is permitted for palliative radiation (\leq 2 weeks of radiotherapy) to non-CNS disease. Participants with \leq grade 2 neuropathy, anemia, and/or alopecia may be eligible.
5. Is currently participating in or has participated in a study of an investigational agent or investigational device within 4 weeks prior to the first dose of study treatment. (i.e. must be 4 weeks after the last dose of the previous investigational agent).
6. Has received a live vaccine within 30 days prior to the first dose of study drug. Seasonal influenza vaccines for injection are generally killed virus vaccines and are allowed; however, intranasal influenza vaccines (e.g., FluMist®) are live attenuated vaccines and are not allowed.
7. Has a known additional malignancy that is progressing or requires active treatment. Exceptions include basal cell carcinoma of the skin, squamous cell carcinoma of the skin, or carcinoma in situ (e.g. breast carcinoma, cervical cancer in situ) that have undergone potentially curative therapy.
8. Has known CNS metastases and/or carcinomatous meningitis.
9. Has symptomatic ascites or has required a paracentesis in the last 12 weeks
10. Has known hypersensitivity to nivolumab, copanlisib, or any ingredients in the formulation of these study drugs.
11. Has a diagnosis of immunodeficiency or is receiving chronic systemic steroid therapy (in dosing exceeding 10 mg daily of prednisone equivalent) or any other form of immunosuppressive therapy within 7 days prior to the first dose of study drug.
12. Has active autoimmune disease that has required systemic treatment in the past 12 months, or a documented history of clinically severe autoimmune disease, or a syndrome that requires systemic steroids or immunosuppressive agents. Subjects with vitiligo or resolved childhood asthma/atopy are exceptions. Intermittent use of bronchodilators or local steroid injections are not excluded. Replacement therapy (e.g. thyroxine, insulin, or physiologic corticosteroid replacement therapy for adrenal or pituitary insufficiency, etc.) is not considered a form of systemic treatment. Autoimmune diagnoses not listed must be approved by the protocol chair.

13. Has a history of (non-infectious) pneumonitis that required steroids or has current pneumonitis.
14. Has an active infection requiring systemic therapy.
15. Has a known history of Human Immunodeficiency Virus (HIV) infection.
16. Has a known history of Hepatitis B (HBsAg reactive) or active Hepatitis C virus infection (HepCAb followed by HepC RNA if Ab test is positive).
17. CMV PCR positive
18. Has a history or concurrent condition of interstitial lung disease or severely impaired lung function (as judged by the investigator)
19. Has Type I diabetes or Type II diabetes requiring treatment with a sulfonylurea, meglitinide, or insulin.
20. Uncontrolled cardiovascular disease
 - a. Congestive heart failure > New York Heart Association (NYHA) class 2
 - b. Unstable angina (symptoms at rest), new-onset angina (within the last 3 months).
 - c. Myocardial infarction less than 6 months before start of test drug
 - d. Uncontrolled arterial hypertension despite optimal medical management
21. Use of anti-arrhythmic therapy (beta blockers or digoxin are permitted)
22. Use of CYP3A4 inhibitors and inducers within 2 weeks of starting study drug and throughout treatment. Examples of inhibitors of CYP3A4: ketoconazole, itraconazole, clarithromycin, ritonavir, indinavir, nelfinavir and saquinavir. Examples of inducers of CYP3A4: rifampin, phenytoin, carbamazepine, phenobarbital, St. John's Wort. See **Table 7** for complete list.
23. Arterial or venous thrombotic or embolic events such as cerebrovascular accident (including transient ischemic attacks), deep vein thrombosis, or pulmonary embolism within 3 months before the start of study medication
24. Non-healing wound, ulcer, or fracture
25. Patients with evidence or history of bleeding diathesis. Any hemorrhage or bleeding event \geq CTCAE Grade 3 within 4 weeks prior to the start of study medication
26. Had a blood or platelet transfusion within 7 days of Cycle 1 Day 1 treatment
27. Seizure disorder requiring anti-seizure medication
28. Has known psychiatric or substance abuse disorders that would interfere with cooperation with the requirements of the trial.

29. Has a history or current evidence of any condition, therapy, or laboratory abnormality that might confound the results of the study, interfere with the subject's participation for the full duration of the study, or is not in the best interest of the subject to participate, in the opinion of the treating investigator.
30. Is pregnant or breastfeeding, or expecting to conceive or father children within the projected duration of the study, starting with the screening visit through 6 months after the last dose of trial treatment
31. Is a prisoner or is compulsorily detained

3.3 Inclusion of Women and Minorities

Both men and women of all races and ethnic groups are eligible for this trial.

4. TREATMENT PLAN

4.1 Registration and Enrollment

Eligible patients will be entered on study centrally at the Sidney Kimmel Comprehensive Cancer Center at the Johns Hopkins University by the Lead Study Coordinator. All sites should contact the Lead Study Coordinator to verify ongoing study enrollment. The Registration Form and Eligibility Checklist will be supplied to each participating site. If a patient does not receive protocol therapy following registration, the patient's registration on the study may be canceled. The Study Coordinator should be notified of cancellations as soon as possible.

de-identified documents should be completed and sent to

- Registration Form
- Signed patient consent form with printed patient name and DOB redacted
- Eligibility Checklist
- Participating Sites: copy of required screening tests, scans, and notes used to verify eligibility
- Coordinating Center (Johns Hopkins University): required screening tests, scans, and notes will be verified for eligibility through internal electronic clinic system.

The Research Nurse or Lead Study Coordinator at the participating site will then e-mail the Protocol Chair to verify eligibility. To complete the registration process, the Lead Study Coordinator will:

- Assign a patient study number
- Register the patient on the study
- Fax or e-mail the patient study number to the participating site
- Call or e-mail the research nurse or data manager at the participating site and verbally confirm registration.

4.2 Agent Administration

There will be two phases in this study: A Phase I dose-finding stage followed by a Phase II expansion.

Copanlisib will be administered as a 60 minute IV infusion (-5min/+10min) at the doses and days shown in **Table 1** and **Table 2** below. Subjects should be observed for a minimum of 30 minutes after administration of Copanlisib prior to administration of nivolumab.

Nivolumab 480 mg will be administered as a 30 minute IV infusion (-5min/+10min) on Day 1 of each 28 day cycle.

The Pharmacy Manual contains specific instructions for the preparation and administration of these study drugs.

[figure not shown]
Study treatment should be administered after all procedures/assessments have been completed for that visit as detailed on the Study Calendar (**Section 8**). Study treatment may be administered up to 3 days before or after the scheduled Day 1 of each cycle, up to 1 day after the scheduled Day 8, or up to 3 days after Day 15 of each cycle due to administrative reasons as long as there is a minimum of 7 days between copanlisib infusions.

All trial treatments will be administered on an outpatient basis.

Phase I – Dose De-Escalation

Phase I will use a standard 3+3 design. The initial dose being tested is the recommended phase 2 dose of both study drugs as single agents, so the doses of copanlisib and nivolumab will not escalate higher than dose level 1. However, if the recommended phase II dose (RP2D) is exceeded in dose level 1, the dose of copanlisib will de-escalate as indicated below in Table 1. A maximum of 18 eligible subjects will be enrolled into this phase. All patients enrolled at each dose level will be evaluated for dose limiting toxicities (DLTs) during the first 28 day cycle for the purpose of determining the RP2D when given concurrently with nivolumab. DLTs and dose de-escalation rules are defined in **Section 4.3** and **Table 3**, respectively.

[figure not shown]
Table 1 – Phase I Dose Levels and Regimen (listed in order of administration)

Phase II – Expansion Cohorts

Phase II will enroll patients with mismatch-repair proficient colorectal cancer with known PI3K-mutation status. 21 patients will be enrolled into Cohort A (PIK3CA mutation) and 21 patients will be enrolled into Cohort B (PIK3CA WT). Both cohorts will receive the same treatment regimen. The dose of copanlisib given in Phase II will be the RP2D determined during Phase I of this study.

Table 2 - Phase II Regimen (listed in order of administration)

4.3 Dose Limiting Toxicities

Dose limiting toxicities (DLTs) are defined as any AE occurring within the first cycle of treatment that is temporally related to study drug administration, which is not due to the subject's underlying malignancy, for which there is no clear evidence for an alternative etiology, and that meets one of the following NCI CTCAE criteria:

Hematologic Toxicities

- Grade 4 anemia
- Grade \geq 3 neutropenia lasting \geq 14 days
- Grade \geq 3 febrile neutropenia
- Grade 4 thrombocytopenia, or Grade 3 thrombocytopenia with clinically significant bleeding

Other Toxicities

- Treatment-related \geq grade 4 AEs, except transient hyperglycemia
- Grade \geq 3 Pneumonitis or recurrent Grade 2 pneumonitis
- Grade \geq 3 Nephritis
- Grade \geq 3 elevated AST, ALT
- Grade \geq 2 eye pain or reduction of visual acuity that does not respond to topical therapy and does not improve to \leq grade 1 severity within 2 weeks of starting therapy, or requires systemic therapy
- Any other Grade \geq 3 toxicities except
 - Grade 3 nausea, vomiting, or diarrhea that resolves to Grade \leq 1 within 7 days, with or without appropriate supportive therapy
 - Grade 3 rash that resolves to Grade \leq 2 within 7 days
 - Grade 3 fatigue that resolves to \leq Grade 2 within 14 days

- Grade 3 transient hypertension and transient hyperglycemia
- Grade ≥ 3 laboratory abnormalities that, in the judgment of the investigator, are not clinically significant
- Asymptomatic amylase/lipase elevation

Unexpected Grade 3 or greater laboratory abnormalities should be repeated within 24-72 hours if clinically indicated and monitored as necessary to determine if event meets toxicity criteria.

Table 3 – Dose De-Escalation Rules

Number of Patients with DLT at a Given Dose Level	Dose De-Escalation Decision Rule (dose levels found in Table 1)
0-1 out of 3	Enter 3 more patients at this dose level 
 • If ≤ 1 of 6 subjects in this cohort experience a DLT, this is the recommended phase II dose (RP2D) • If ≥ 2 of 6 patients in this cohort experience a DLT, this dose level exceeded the RP2D. 3 patients will be entered at the next lower dose level.
≥ 2 out of 3	This dose level exceeded the RP2D. 3 additional patients will be entered at the next lower dose level.

4.4 Dose Modification and Toxicity Management

4.4.1 Dosing Delays and Modifications

Study treatments are scheduled on a 3 weeks on, 1 week off schedule.

- Start of a treatment cycle (Day 1) will be delayed for toxicity until retreatment criteria are met. The Principal Investigator must approve retreatment if delays last longer than 1 week. If delays are required due to toxicity related to one study drug but not the other, all study treatment will be delayed.
- If the day 8 or day 15 dose of copanlisib needs to be delayed longer than 2 days due to toxicity, the dose(s) should be skipped and the remainder of the cycle continued once retreatment criteria are met. The intention here is to keep the length of each cycle to 4 weeks, when possible. Skipped doses will be documented in the study database.

There will be no dose reductions to nivolumab. Dose reductions to copanlisib will use the dose levels outlined in **Table 1** and dose reduction criteria outlined in **Table 4**. If a patient is already receiving the lowest dose level of copanlisib and meets criteria for further decrease, study treatment will be discontinued permanently. There will be no dose re-escalation for DLTs. Dose re-escalation may be allowed for non-DLTs at the PI's discretion after patient has fully recovered from the toxicity and in the absence of any other

adverse events that require dose-reduction, with the exception of non-infectious pneumonitis.

Dosing of study therapy will be delayed for the following criteria (or **Table 4** criteria):

- AST/ALT $>3 \times$ ULN
- Total bilirubin $> 1.5 \times$ ULN ($> 2.0 \times$ ULN for subjects with Gilbert's syndrome)
- Creatinine $> 1.5 \times$ ULN or GFR < 40 mL/min/1.73 m²
- Hemoglobin < 8 g/dL
- ANC < 1250 /uL (day 1) and < 1000 (days 8 and 15) – hold both study drugs
- Platelets $< 75 \times 10^3$ /uL
- Fasting Glucose (Cycle 1 Day 1) >125 mg/dL (non-diabetic patients) or ≥ 160 mg/dL (diabetic patients)
- Fasting glucose (all other days) > 160 mg/dL
- CMV PCR > 500 IU/mL (tested each cycle for cycles 1-6, and every 3 months thereafter)
- Any Grade ≥ 2 non-skin, nivolumab-related adverse event, with the following exceptions:
 - Grade 2 fatigue
 - Grade 2 lab abnormalities
 - Grade 2 hypothyroidism or thyroiditis
- Any Grade ≥ 3 skin nivolumab-related AE
- Any Grade ≥ 3 nivolumab-related laboratory abnormality with the following exceptions:
 - Grade 3 lymphopenia
 - Any Grade ≥ 3 drug-related amylase or lipase abnormality that is not associated with symptoms or clinical manifestations of pancreatitis
 - Isolated grade 3 or 4 electrolyte imbalances/abnormalities that are not associated with clinical sequelae and are corrected with supplementation/appropriate management
- Any AE, laboratory abnormality, or inter-current illness which, in the judgment of the investigator, warrants delaying the dose of study medication.

Table 4 - Dose modification and toxicity management guidelines for AEs associated with copanlisib

Drug-related AEs	Grade (CTCAE v5.0) or measurement	Action taken to study drugs	Retreatment Dose Level	AE management	Monitor and follow-up
Hyperglycemia	Grade 1: Asymptomatic glucose above baseline with no medical intervention	Withhold until pre-infusion glucose is <160 mg/dL (fasting)	No change in dose	
 Hydration as appropriate May follow without glucose-lowering tx if repeated glucose value is decreasing and hydration status is normal 	
 Repeat glucose testing Endocrinologist consult recommended Consider prophylaxis with oral glucose lowering tx for next dose: Recommended (preferred order): SGLT2 inhibitor, DPP4 inhibitor, metformin, and/or thiazolidinedione Not recommended: Use of sulphonylurea/ metaglinides, insulin secretagogues to manage increased glucose levels post drug infusions
	Symptomatic or persisting glucose >250mg/dL ¹	Withhold until pre-infusion glucose is <160 mg/dL (fasting)	No change in dose	
 Hydration as clinically appropriate Glucose-lowering medication should be given: Recommended (preferred order): SGLT2 inhibitor, DPP4 inhibitor, metformin, and/or thiazolidinedione Not recommended: Use of sulphonylurea/ metaglinides, insulin secretagogues to manage increased glucose levels post drug infusions 	
 Assess hydration status Repeat glucose testing Consult with endocrinologist Consider prophylaxis with oral glucose lowering tx for next dose: Recommended (preferred order): SGLT2 inhibitor, DPP4 inhibitor, metformin, and/or thiazolidinedione Not recommended: Use of sulphonylurea/ metaglinides, insulin secretagogues to manage increased glucose levels post drug infusions
	Persistent glucose >500 mg/dL ¹	Withhold until pre-infusion glucose is <160 mg/dL (fasting)	Decrease by one dose level if repeated after 2 infusions. Discontinue if persistent at lowest dose level after at least one cycle, despite optimal tx and consult with diabetes specialist.		
	Max glucose >200mg/dL on subsequent days after infusion	N/A	N/A		
 Treatment with glucose-lowering medication per local standards Recommended (preferred order): SGLT2 inhibitor, DPP4 inhibitor, metformin, and/or thiazolidinedione Not recommended: Use of sulphonylurea/ metaglinides, insulin secretagogues to manage increased glucose levels post drug infusions

Drug-related AEs	Grade (CTCAE v5.0) or measurement	Action taken to study drugs	Retreatment Dose Level	AE management	Monitor and follow-up
Arterial Hypertension	Pre-dose BP >150/90 mmHg	Withhold ²	No change in dose	
 Consider BP-lowering medication 	
 Measure BP every 5-10 minutes (no more than 4 measurements) until acceptable for treatment.
	BP during infusion >160/100 mmHg	Interrupt if having symptoms attributable to hypertension ²	Next dose reduced by one dose level at PI's discretion	
 Initiate BP lowering medication according to standard of care 	
 Monitor BP as clinically indicated until <150/90.
	Post-dose BP >160/100 mmHg ³	N/A			
 Monitor BP as clinically indicated.
	Grade 4	Permanently discontinue	N/A		
Non-infectious Pneumonitis	Grade 2	Withhold	Decrease by one dose level		
	Grade 3 or 4 or recurrent Grade 2	Permanently discontinue	N/A		
Infections	Grade 3 or higher	Withhold	N/A		
	Suspected PJP infection of any grade	Withhold. Resume once infection resolves	N/A	If confirmed PJP, treat infection until resolution	Treat with concomitant PJP prophylaxis after resolution/ restarting of copanlisib
Dermatologic / Cutaneous AEs	Grade 2 ³	Withhold	1 st : no dose change 2 nd -3 rd : decrease by one dose level 4 th : discontinue		
	Grade 3 ³	Withhold	1 st -2 nd : decrease by one dose level 3 rd : discontinue		
	Grade 4	Permanently discontinue	N/A		
Hematological toxicity ⁴	Grade 2 neutropenia or thrombocytopenia on day 1 of each cycle	Withhold	No change in dose		

Table 4 - Dose modification and toxicity management guidelines for AEs associated with copanlisib					
Drug-related AEs	Grade (CTCAE v5.0) or measurement	Action taken to study drugs	Retreatment Dose Level	AE management	Monitor and follow-up
	Grade ≥ 3	Withhold	Decrease by one dose level at the PI's discretion	
 • Treatment with transfusion or growth factors allowed at PI's discretion 	
Other non-hematological toxicities	Grade 3	Withhold	1 st : no dose change 2 nd -3 rd : decrease by one dose level 4 th : discontinue		
	Grade 4 or any toxicity requiring delay for >21 days	Permanently discontinue	N/A		

 1. Persistent occurrence is defined as repeated post-infusion blood glucose measurements taken at different times during the cycle despite optimal glucose-lowering therapy in consultation with endocrinologist 2. Infusion may proceed/resume on scheduled day if BP recovers to <150/90 mmHg for 2 consecutive measurements and symptoms (if present) resolve. 3. Despite maximum supportive therapy 4. Thrombocytopenia, neutropenia, febrile neutropenia, anemia, INR or PTT with bleeding 
General instructions:
 
 • For situations where drug is withheld due to a copanlisib-related AE, treatment can be resumed after AE has been reduced to Grade 1 or 0 unless otherwise indicated. Treatment should be permanently discontinued if AE does not resolve within 12 weeks of last dose. • If patient is already on lowest dose level and meets criteria for further decrease, study drug will be discontinued permanently. • Dose re-escalation may be allowed at the PI's discretion after patient has fully recovered from the toxicity and in the absence of any other adverse events that require dose-reduction, with the exception of non-infectious pneumonitis. • Abbreviations: SGLT2 = Sodium/Glucose co-transporter 2; DPP4 = Dipeptidyl peptidase 4; PJP= pneumocystis jiroveci pneumonia 					

In order to standardize the management of AEs for all subjects, treatment management algorithms are included in **Appendix C**. Additional AE treatment management algorithms included in the nivolumab IB might be considered for individual cases.

Subjects who require a delay in study treatment should be re-evaluated weekly or more frequently if clinically indicated and resume dosing when re-treatment criteria are met.

Subjects may resume treatment with study drug when the nivolumab-related AE(s) resolve to grade ≤ 1 or baseline value, with the following exceptions:

- Subjects may resume treatment in the presence of grade 2 fatigue.
- Subjects who have not experienced a Grade 3 drug-related skin AE may resume treatment in the presence of Grade 2 skin adverse event
- Treatment-related pulmonary toxicity, diarrhea, or colitis must have resolved to baseline before treatment is resumed.
- Treatment-related endocrinopathies adequately controlled with only physiologic hormone replacement may resume treatment, which include grade 2 hyperglycemia, hypothyroidism and thyroiditis.

Subjects should be permanently discontinued if AE does not resolve within 12 weeks of last dose or corticosteroids cannot be reduced to ≤ 10 mg prednisone or equivalent per day within 12 weeks.

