1.5 Study Design

This is a multi-center, open-label, Phase I/II study. Phase 1 consists of a 3+3 dose de-escalation design to determine the dose of copanlisib for use in combination with nivolumab. Approximately 6-18 subjects with solid tumors will be treated in Phase I and will be monitored for dose limiting toxicities (DLTs) through their first cycle of treatment. Complete information on the definition of DLTs and dose de-escalation rules can be found in **Section 4.3**.

The Phase II portion of the study will evaluate the safety and clinical activity of copanlisib and nivolumab in two cohorts of patients with previously treated metastatic colon cancer. Cohort A will enroll patients with PI3K mutation and Cohort B will enroll patients with wildtype PI3K status. Twenty-one patients are targeted for enrollment in each cohort, for an approximate total of 42 patients in Phase II. Enrollment in Phase II will be initiated once the recommended phase II dose (RP2D) has been determined in Phase I.

For all patients, the study will consist of a screening period, a treatment period, and a follow-up period. Screening evaluations will be done within 28 days prior to the start of study treatment.

Each treatment cycle is 28 days. Patients in both Phase I and Phase II will receive nivolumab on Day 1 of each cycle (every 4 weeks) and copanlisib on either Day 1, Day 8, and Day 15 of each cycle (3 week on, one week off) or on Day 1 and 15 of each cycle (every 2 weeks), depending on the dose level and RP2D. Complete information on study drug administration, schedule, and dosing can be found in **Section 4.2**.

Phase II enrollment will be carried out in 2 stages so that the study can terminate early if the combination of copanlisib and nivolumab is not sufficiently effective. In the first stage, 12 subjects will be accrued to each cohort. If there are no responders among the first 12 patients, the study will be terminated for futility. Otherwise, 9 additional patients will be accrued for a total of 21 treated subjects. If ≥ 3 out of the 21 patients have a response, then the trial will be considered a success for that cohort.

Clinical and immune responses will be evaluated at baseline and during treatment through tumor assessments, biopsies, and PBMC and plasma collection. Tumor assessments will be made using RECIST 1.1.

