4.4.4 Additional Toxicity Monitoring and Prevention

4.4.4.1 Glucose and Diet Monitoring

Period	Fasting \geq 12 h required before first glucose measurement	Pre-dose glucose levels
Day 1 of Cycle 1	Yes	<125 mg/dL (non-diabetic patients) <160 mg/dL (diabetic patients)
Subsequent infusions after Cycle 1 Day 1	Yes	<160 mg/dL (fasting) <200 mg/dL (non-fasting)

Fasting refers to a \geq 12 hour fast. Non-fasting status includes any caloric intake such as meals, juice, snack, as well as other caloric intake not consistently called a meal.

From Cycle 1 Day 1 onwards, glucose measurements may be done either by laboratory analysis or in capillary blood.

Because of its inhibitory effect on the PI3K α -isoform, which is implicated in insulin metabolism, copanlisib infusions could be associated with a temporary increase in blood glucose. Addition of a meal in close proximity to copanlisib infusion may exacerbate glucose increase.

On infusion days a low calorie or low carbohydrate diet is recommended. It is recommended that timing and content of caloric intake as well as additional glucose testing (if clinically indicated) on infusion days is monitored by the investigators based on glucose response patterns during prior treatment days. Consultation with a diabetologist or endocrinologist is advised.

All glucose measurements, oral glucose lowering medication and/or insulin administration, if applicable, fasting/non-fasting status, and meal intake timing on infusion days will be collected as part of the clinical source documentation.

Glucose monitoring on study

Management of hyperglycemia and dose delay parameters are outlined in **Table 4**

The following assessments should be performed on Day 1, 8, and 15 of each cycle before receiving copanlisib unless otherwise specified:

- Patients should be fasting for at least 12 hours prior to the pre-dose glucose measurement. For details on fasting requirements and glucose measurement during C1D1 please refer to **Table 6**
- Blood glucose will be measured at 0 hours (pre-dose) and 1 hour after completion of copanlisib (+/- 15min) infusion. If 1 hour post-infusion blood glucose is \geq 35 mg/dL higher than pre-dose level, recheck in another hour (2 hours post-infusion) to ensure decline in blood glucose. Additional measurements to be performed as clinically indicated.

NOTE: If patient needs to take a low glycemic meal, then glucose test should be taken prior to meal intake.

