7.1 Tumor Tissue

Patients in both phases of the study will have paired biopsies – one prior to treatment and one after six weeks on therapy (4-6 cores per time point). This will be prior to Cycle 2 Day 15 treatment, after two doses of nivolumab and three or five doses of copanlisib (depending on the dose level). Patients will also be asked for an optional biopsy at the time of progression.

Tumor biopsy will not be performed if the tumor is not accessible or if biopsy is considered not in the patient's best interest.

Attempts will be made to obtain archived tissue samples from all subjects. Archived FNA biopsy samples do not contain sufficient tissue and will not be collected.

We will assess tumor immune infiltrate using immunohistochemistry (IHC) and flow cytometry of disaggregated tumor samples. Expression of PD-L1 and of a series of biomarkers will be assessed by IHC. CD8+ T cells will be enriched by magnetic separation from disaggregated tumor samples and stimulated *ex vivo* to query markers of T cell exhaustion and cytokine production. We will also use single cell RNASeq for an unbiased assessment not only of cellular composition but also of functional status as assessed by gene expression profiles. From single cell expression data, we hope to identify gene expression profiles of tumor cells that are correlated with response to therapy.

Tumor Sample Requirements:

Slides

H&E

10 unstained FFPE

Tissue

50mg fresh (flow cytometry)

50mg fresh (*ex vivo* T cell stimulation)

25 mg fresh/frozen (single cell RNASeq)

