8. STUDY SCHEDULE

8.1 Study Calendar – Phase I

Procedure	Baseline ¹ (-28 to 0)	Treatment (1 cycle = 28 days)						EOT ²¹ 30 days (+/-4 days) after last study drug	Survival Follow-Up ²² Q12 weeks (± 2 weeks)
		Cycle 1			Cycle 2 and higher				
		D1 (±3 days)	D8 (+1 day)	D15 (+3 days)	D1 (±3 days)	D8 (+1 day)	D15 (+3 days)		
Administrative Procedures									
Informed Consent	X								
Inclusion/Exclusion Criteria	X								
Demographics and Med Hx ²	X								
Copanlisib		X	X	X	X	X	X		
Nivolumab		X			X				
Post-study anticancer therapy and survival status									X
Clinical Assessments									
Physical Examination, ECOG ³	X	X	X	X	X		X	X	
Vital Signs ⁴	X	X	X	X	X	X	X	X	
Blood Pressure (infusion days) ⁵		X	X	X	X	X	X		
Weight	X	X			X			X	
Height (may be from prior visit)	X								
Review Adverse Events		X	X	X	X	X	X	X	
Con Med Review	X	X	X	X	X	X	X	X	
Laboratory Assessments									
CBC with Differential ^{6, 16}	X	X	X	X	X	X	X	X	
Chemistry Panel ^{7, 16}	X	X	X	X	X	X	X	X	
Glucose ⁸		X	X	X	X	X	X		
Hemoglobin A1C ¹⁶	X				X ⁹			X	
Lipid Panel ^{10, 16}	X	X	X	X	X(even cycles)			X	
TSH ^{11, 16}	X	X		X	X		X	X	
PT, INR and aPTT ¹⁶	X								
HBsAg, HCV Ab, HIV ¹²	X								
CMV PCR ^{13, 16}	X				X				
Pregnancy Test ^{14, 16}	X	X			X			X	
Urinalysis ^{15, 16}	X				X(even cycles)				
Urine protein:creatinine ratio (UPCR)	X								
12-lead ECG	X							X	
MUGA or echocardiogram ¹⁷	X							X	
CEA	X	X			X			X	
Efficacy Assessments									
Tumor Imaging ¹⁸	X				X(odd cycles)			X	
Tissue and Blood for Correlative Studies									
Fresh Tumor Biopsy ¹⁹	X						X	X	
Archival Tumor Sample	X								
Blood for PBMC (180cc) ^{20, 16}		X		X	X(odd cycles)			X	

Procedure	Baseline ¹ (-28 to 0)	Treatment (1 cycle = 28 days)						EOT ²¹ 30 days (+/-4 days) after last study drug	Survival Follow-Up ²² Q12 weeks (± 2 weeks)
		Cycle 1			Cycle 2 and higher				
		D1 (±3 days)	D8 (+1 day)	D15 (+3 days)	D1 (±3 days)	D8 (+1 day)	D15 (+3 days)		
Blood for plasma (20 cc) ^{20, 16}		X		X	X(odd cycles)			X	

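### Sections 1.5 and 7.1 allow two copanlisib schedules by dose level, but the opening of 4.4.1 and the copanlisib rows of both calendars show only Days 1, 8 and 15

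*Combined protocol and SAP*

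**What the plan says.** Two sections describe a schedule that varies with dose level.

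- Section 1.5 (Study Design) sets the cycle length ("Each treatment cycle is 28 days") and gives two options for copanlisib: Days 1, 8 and 15, which it labels three weeks on and one week off, "or on Day 1 and 15 of each cycle (every 2 weeks), depending on the dose level and RP2D".
- Section 7.1 (Tumor Tissue) places the on-treatment biopsy before the Cycle 2 Day 15 treatment, "after two doses of nivolumab and three or five doses of copanlisib", and says that the number depends on dose level.

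Three other places show one schedule only.

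- Section 4.4.1 opens with "Study treatments are scheduled on a 3 weeks on, 1 week off schedule". Its delay rule then refers to a Day 8 or Day 15 dose without mentioning levels that have no Day 8 dose.
- The copanlisib row of calendar 8.1 (Phase I) reads "Copanlisib X X X X X X": Days 1, 8 and 15 of Cycle 1, and the same days in Cycle 2 and higher. No footnote is attached.
- The copanlisib row of calendar 8.2 (Phase II) is marked in the same way, also without a footnote.

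Section 4.2 (Agent Administration) says that the doses and days are those in Tables 1 and 2. The contents of both tables are missing from the public text. Section 4.4.1 also says that copanlisib dose reductions use the Table 1 levels.

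**The concern.** The number of infusions in a cycle should be the same wherever a site looks it up. Here the design section and the biopsy section imply that at least one dose level has no Day 8 infusion, while the calendars and the lead-in to the delay rules show a Day 8 infusion without exception. The calendars do qualify other conditional entries (even cycles only, odd cycles only, a footnote for HbA1c), so an unqualified mark on Day 8 is naturally read as applying to everyone.

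At stake is an unplanned third infusion per cycle at a Day 1/15 level. If such a level were opened in Phase I, the extra infusion would fall inside the 28-day window in which dose-limiting toxicities are counted. It would also change the copanlisib exposure behind the paired biopsy.

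**Working it through.** **Inputs.** Cycle length 28 days (1.5). Schedule A: Days 1, 8, 15 (1.5). Schedule B: Days 1, 15 (1.5). Biopsy before Cycle 2 Day 15 (7.1). Nivolumab on Day 1 of each cycle (1.5, 4.2). Minimum gap between copanlisib infusions 7 days (4.2).

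**Step 1: reproduce the figures in 7.1.** Count the infusions scheduled strictly before Cycle 2 Day 15.

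- Schedule A: 3 in Cycle 1, plus Days 1 and 8 of Cycle 2 = 3 + 2 = 5.
- Schedule B: 2 in Cycle 1, plus Day 1 of Cycle 2 = 2 + 1 = 3.
- Nivolumab: 1 + 1 = 2.
- Timing: Cycle 2 Day 15 is study day 28 + 15 = 43, which is (43 − 1)/7 = 6 weeks after the first dose.

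All of these agree with 7.1: two doses of nivolumab, three or five of copanlisib, six weeks. So the two-infusion schedule is not a stray phrase in 1.5; 7.1 counts doses on the same basis.

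**Step 2: set the places side by side.**

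| Place | Infusion days shown | Per cycle | Before Cycle 2 Day 15 |
|---|---|---|---|
| 1.5 | 1, 8, 15 or 1, 15, by dose level | 3 or 2 | 5 or 3 |
| 7.1 | by dose level | – | 5 or 3 |
| 4.4.1, opening sentence | three weeks on, one off | 3 | 5 |
| 8.1, copanlisib row | 1, 8, 15 | 3 | 5 |
| 8.2, copanlisib row | 1, 8, 15 | 3 | 5 |
| 4.2, Tables 1 and 2 | not visible | – | – |

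**Step 3: size of the conflict at a Day 1/15 level.** 3/2 − 1 = 0.50, so 50% more copanlisib per cycle at the same dose per infusion. Over six cycles the count is 6 × 3 = 18 against 6 × 2 = 12.

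**Step 4: would another rule stop a Day 8 infusion?** With Days 1, 8 and 15 the gaps are 7, 7 and 14 days. The 7-day minimum in 4.2 is met, so that rule would not block it.

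**Step 5: who could be affected?** The visible text does not say which level or levels use Days 1 and 15, or which schedule goes with the recommended Phase II dose. The range therefore runs from some Phase I or dose-reduced patients only, to all 42 Phase II patients if the recommended dose is a Day 1/15 level.

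**The case against.** The best defence is that the protocol does name a controlling source. Section 1.5 sends the reader to 4.2 for complete information on schedule and dosing, and 4.2 takes the doses and days from Tables 1 and 2. Section 4.2 cites the calendar only for the procedures to complete before treatment. On that reading the calendar is a superset of possible visits, and nothing says that it overrides the tables. The opening sentence of 4.4.1 cannot be a literal dosing order either, because it speaks of study treatments in general and nivolumab is given on Day 1 only.

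Much of this stands, and it limits the consequence. It does not remove the disagreement, because neither that sentence nor the copanlisib rows point to the tables or carry an exception.

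A reader might also infer more than the documents support:

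- *That 4.4.1 ignores the dosing tables.* It does not. It uses the Table 1 levels for dose reductions, so for dose-reduced patients it leads to the table that 4.2 says sets the days.
- *That patients reduced for toxicity will receive the extra dose, or that the recommended Phase II dose will be distorted.* The first requires the Day 1/15 level to lie below the level the patient was on. The second requires that level to have been opened in Phase I and its patients dosed contrary to Table 1. None of this can be established without the tables.
- *That the Day 8 glucose and blood pressure entries also need changing.* These checks are already tied to copanlisib infusions: the blood pressure row is labelled for infusion days, and the glucose times are pre-dose and post-infusion. Without a Day 8 infusion they have no trigger.

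**Conclusion.** The point holds as an internal inconsistency in operational dosing instructions. Sections 1.5 and 7.1 provide for dose levels with two infusions per cycle; the opening of 4.4.1 and the copanlisib rows of 8.1 and 8.2 show three throughout. At a Day 1/15 level the difference is one infusion per cycle.

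The count of five or three doses rests only on visible text. The consequence is conditional: it needs a patient at a Day 1/15 level and a site working from the calendar or the 4.4.1 lead-in instead of Tables 1 and 2. It is a risk to be closed, not evidence that anyone would be dosed wrongly. For Phase I, all that can be said is that an extra infusion at such a level would fall within the window for dose-limiting toxicities. This should be corrected because it concerns how many infusions a patient receives and the correction is nearly free.

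**What to change.** Reconcile 1.5, 4.2 (Tables 1 and 2), 4.4.1, 7.1 and the copanlisib rows of 8.1 and 8.2 so that all give the same infusion days for each dose level. One way is to have the opening sentence of 4.4.1 and the two copanlisib rows refer to Tables 1 and 2 for the infusion days. The study team must settle which days belong to which level; this review takes no position on that. No separate edit to the glucose or blood pressure entries is needed.

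The cost is one footnote in each calendar and one sentence in 4.4.1, plus a check that 1.5 and 7.1 agree with the tables. Sample size and analysis are unaffected.
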